# **5 Appendix**

This will be used later for drafting CSR Appendix 16.1.9.

## 5.1 Imputation rules

### 5.1.1 Study drug

The following rule should be used for the imputation of the dose end date for dabrafenib:

**Scenario 1:** If the dose end date is completely missing and there is no EOT page and no death date, the patient is considered as on-going:

The patient should be treated as on-going and the cut-off date should be used as the last dosing date.

**Scenario 2:** If the dose end date is completely or partially missing and the EOT page is available:

Case 1: The dose end date is completely missing, and the EOT completion date is complete, then this latter date should be used.

Case 2: Only Year(yyyy) of the dose end date is available and yyyy < the year of EOT date:

**Use Dec31yyyy**

Case 3: Only Year(yyyy) of the dose end date is available and yyyy = the year of EOT date:

**Use EOT date**

Case 4: Both Year(yyyy) and Month (mm) are available for dose end date, and yyyy = the year of EOT date and mm < the month of EOT date:

**Use last day of the Month (mm)**

All other cases should be considered as a data issue and the statistician should contact the data manager of the study.

After imputation, compare the imputed date with start date of treatment, if the imputed date is < start date of treatment:

**Use the treatment start date**

Patients with missing start dates are to be considered missing for all study treatment component related calculations and no imputation will be made. If start date is missing then end-date should not be imputed.

### 5.1.2 AE date imputation

The following missing dates will not be imputed

- Missing AE start dates
- AE start dates missing the year
- Partial/missing AE end dates

For other type of missing dates, rules specified in Tables 5-1 to 5-3 will be used

**Table 5-1 AE/Treatment Date Abbreviations**

	Day	Month	Year
Partial Adverse Event Start Date	<not used>	AEM	AEY

	Day	Month	Year
Treatment Start Date (TRTSTD)	<not used>	TRTM	TRTY

Table 5-2 describes the possible combinations and their associated imputations. The upper text indicates the imputation (NC, A, B, C etc.) and the lower text the relationship of the AE start date to the treatment start date (TRTSTD).

**Table 5-2 Imputation algorithm**

	AEM MISSING	AEM < TRTM	AEM = TRTM	AEM > TRTM
AEY MISSING	NC Uncertain	NC Uncertain	NC Uncertain	NC Uncertain
AEY < TRTY	( D ) Before TRTSTD	( C ) Before TRTSTD	( C ) Before TRTSTD	( C ) Before TRTSTD
AEY = TRTY	( B ) Uncertain	( C ) Before TRTSTD	( B ) Uncertain	( A ) After TRTSTD
AEY > TRTY	( E ) After TRTSTD	( A ) After TRTSTD	( A ) After TRTSTD	( A ) After TRTSTD

The legend to the above table is shown in Table 5-3.

**Table 5-3 Imputation algorithm legends**

Relationship	
Before TRTSTD	Indicates AE start date prior to Treatment Start Date
After TRTSTD	Indicates AE start date after Treatment Start Date
Uncertain	Insufficient to determine the relationship of AE start date to Treatment Start Date
Imputation calculation	
NC / Blank	No convention/imputation
( A )	01MONYYYY
( B )	TRTSTD+1
( C )	15MONYYYY
( D )	01JULYYYY
( E )	01JANYYYY

Few examples are shown in Table 5-4.

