### **7.3.1.5. Time Period and Frequency of Detecting AEs and SAEs**

The investigator or site staff is responsible for detecting, documenting and reporting events that meet the definition of an AE or SAE.

AEs will be collected from the time the first dose of study treatment is administered until 30 days following discontinuation of study treatment regardless of initiation of a new cancer therapy or transfer to hospice.

SAEs will be collected over the same time period as stated above for AEs. In addition, any SAE assessed **as related** to study participation (e.g., protocol-mandated procedures, invasive tests, or change in existing therapy), study treatment or GSK concomitant medication must be recorded from the time a subject consents to participate in the study up to and including any follow-up contact. All SAEs will be reported to GSK within 24 hours, as indicated in Section 7.3.1.6.

After discontinuation of study treatment, the investigator will monitor all AEs/SAEs that are ongoing until resolution or stabilization of the event or until the subject is lost to follow-up. At any time after 30 days the investigator may report any adverse event that they believe possibly related to study treatment.

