### **On-treatment assessment/event and observation periods**

The overall observation period will be divided into three mutually exclusive segments:

**Pre-treatment period** is defined as from day of patient's informed consent to the day before first administration of study treatment

**On-treatment period** is defined as from date of first administration of study treatment to 30 days after date of last actual administration of study treatment (including start and stop date)

**Post-treatment period** is defined as starting at day 30+1 after last administration of study treatment.

Notes: if data on clock time is available in the clinical database (e.g. for time of blood/urine sample taken, ECG performed, etc. and first study treatment administration), a more precise distinction between pre-treatment and on-treatment periods is encouraged to be used. If dates are incomplete in a way that clear assignment to pre-, on-, post-treatment period cannot be made, then the respective data will be assigned to the on-treatment period.

Safety summaries (tables, figures) include data from the pre-treatment period (to display the baseline status e.g. for ECG) and the on-treatment period, i.e. data from the post-treatment period with the exception of deaths should not be included unless requested from Health Authorities or external committees.

In particular, summary tables for adverse events (AEs) will summarize only on-treatment events, with a start date during the on-treatment period, the so-called *treatment-emergent* AEs.

However, all safety data (including those from the post-treatment period) will be listed and those collected during the pre-treatment and post-treatment period are to be flagged.

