**End date:**

- Imputed date = min (reference end date, DEC 31), if month and day are missing.
- Imputed date = min (reference end date, last day of the Month), if day is missing.
- Reference end date will be start date of study drug.

If the end date is not missing and the imputed start date is after the end date, use the end date as the imputed start date. If both the start date and the end date are imputed and if the imputed start date is after the imputed end date, use the imputed end date as the imputation for the start date

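### SAP 5.1.2 does not check an imputed AE start against the recorded end date, so an event that ended before first dose can be counted as treatment-emergent

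*SAP*

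**What the plan says.** SAP 5.1.2 handles AE start dates with a missing day, or a missing day and month. As the SAP puts it, "Table 5-2 describes the possible combinations and their associated imputations". The table compares the AE month and year with the treatment-start (TRTSTD) month and year. Two cells lead to rule (B): same month and year as treatment start, and month missing in the treatment-start year. Both are labelled uncertain, which Table 5-3 defines as "Insufficient to determine the relationship of AE start date to Treatment Start Date". Rule (B) imputes TRTSTD+1.

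The AE end date appears in 5.1.2 only in the list of dates that are not imputed ("Partial/missing AE end dates"). No step compares it with the imputed start.

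SAP 5.1.3.1 does make that comparison for prior therapies: "If the end date is not missing and the imputed start date is after the end date, use the end date" as the imputed start.

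SAP 2.1.1 decides what is tabulated: "summary tables for adverse events (AEs) will summarize only on-treatment events, with a start date during the on-treatment period". The pre-treatment period runs from "informed consent to the day before first administration of study treatment". Data with incomplete dates go to the on-treatment period when they cannot clearly be placed in one of the three periods.

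Protocol 7.3.1.5 collects AEs from first dose. The exception is serious adverse events (SAEs) related to study participation, study treatment or a sponsor concomitant medication, which "must be recorded from the time a subject consents to participate in the study up to and including any follow-up contact".

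**The concern.** A complete end date can settle what a partial start date leaves open. If the event ended before first dose, it began before first dose. Rule (B) discards that information and gives the event a start that is later than its known end and inside the on-treatment period.

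The SAP drops laboratory, ECG, cardiac imaging and vital-sign outputs (2.8.3, 2.8.4 and section 4), so the AE and SAE tables carry most of the safety result in this close-out report. A related SAE that resolved during screening, for example after the optional extracranial biopsy, could enter both the AE and SAE summaries as treatment-emergent. It would also lose the flag that 2.8.1 gives to listed events starting outside the on-treatment period.

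**Working it through.** **Inputs.** The rules are in SAP Tables 5-2 and 5-3. The example dates are in SAP Table 5-4 (TRTSTD 20OCT2001). The number of patients enrolled, six, is in SAP 3.1. The AE end dates below are assumed for illustration.

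**1. Reproduce the SAP's examples.** All seven rows of Table 5-4 follow from the rules:

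| Partial AE start | Rule | Imputed start |
|---|---|---|
| year missing | none | blank |
| 2000 only | D | 01JUL2000 |
| 2002 only | E | 01JAN2002 |
| 2001 only | B | 21OCT2001 |
| SEP2001 | C | 15SEP2001 |
| OCT2001 | B | 21OCT2001 |
| NOV2001 | A | 01NOV2001 |

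**2. Add a recorded end date to the OCT2001 row.** Let the end be 15OCT2001.
- The true start lies between 1 and 15 October, before the dose on 20 October.
- Rule (B) still gives 20OCT2001 + 1 = 21OCT2001.
- Imputed start minus recorded end: 21 − 15 = 6 days, so the event starts six days after it ended.
- Study day by the SAP 2.1.1 formula: 21 − 20 + 1 = 2. The event is counted as treatment-emergent.

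The row with only the year 2001 behaves the same way: rule (B) gives 21OCT2001 whatever end date is on record.

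**3. Compare with SAP 2.1.1.** Since start ≤ end and end < TRTSTD, it follows that start < TRTSTD. The event is clearly not on-treatment, so the default for unassignable dates does not apply. Rule (B) and 2.1.1 give different answers for this record.

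**4. Apply the 5.1.3.1 guard,** start = min(imputed start, recorded end):
- End 15OCT2001: min(21, 15) gives 15OCT2001, study day 15 − 20 = −5, pre-treatment.
- End 25OCT2001: min(21, 25) leaves 21OCT2001, on-treatment as before.
- End missing: no change, on-treatment by the 2.1.1 convention.
- End 20OCT2001: gives 20OCT2001, Day 1, still on-treatment.

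In general, if end < TRTSTD then min(imputed, end) < TRTSTD. The guard therefore removes every such misclassification and leaves the uncertain cases where the SAP puts them.

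**5. Size.** One subject in six is 1/6 = 16.7 percentage points in an all-subjects column.

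**The case against.** The strongest defence is that rule (B) suits the data collected. AEs are recorded from first dose, so a partial date in the treatment-start month will nearly always belong to a post-dose event. SAP 2.1.1 openly chooses on-treatment for doubtful dates. A harmful case needs a related SAE before dosing, a missing start day despite 24-hour SAE reporting, a complete end date, and resolution before first dose. In six patients that is remote. AEs are also listed per subject with their end dates, so a contradiction could be seen. All of this stands. It limits the severity but does not justify a rule that can contradict a recorded date.

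A reader might infer more, and the documents do not support it:
- **That the algorithm ignores the recorded month.** Table 5-2 is keyed on the month, and rules (A) and (C) keep it. Rule (B) can leave the month only when first dose falls on a month end (31OCT gives 01NOV). The event is then still Day 2 and on-treatment, so no table changes.
- **That imputed dates before consent distort results.** Rules (C) and (D) can do this: consent 20SEP2001, dose 04OCT2001 and AE ddSEP2001 give 15SEP2001. Such events precede first dose wherever the date lands, so they stay out of the treatment-emergent tables and are flagged in the listing.
- **That most partially dated screening events are misclassified.** Where no end date shows resolution before dosing, on-treatment is the SAP's stated convention.
- **That the listings will print zero or negative durations.** The SAP does not say that imputed starts are printed or used to derive duration.

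**Conclusion.** The point holds in a narrow form, and its severity is minor. For an AE with a partial start that falls under rule (B) and a complete end date before first dose, SAP 5.1.2 gives a start after the end and counts the event as treatment-emergent. That conflicts with the assignment rule in SAP 2.1.1.

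The number of affected records is expected to be very small and may be zero; the documents give no count of partial dates. The 16.7-point figure is the effect of one affected subject on an all-subjects percentage, and assumes that all six enrolled patients were dosed and are in the Safety Set. The effect within a cohort would be larger, but the documents do not give the split between cohorts.

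**What to change.** Add one sentence to SAP 5.1.2, mirroring 5.1.3.1: if the AE end date is complete and earlier than the imputed start, set the imputed start to the end date. An event whose end date precedes TRTSTD is then classified as pre-treatment. The cost is one sentence and one line of code, with no change to the handling of truly uncertain dates.

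An optional tidy-up is to use TRTSTD instead of TRTSTD+1 in rule (B). The on-treatment period includes the first-dose date, so events stay on-treatment, and TRTSTD always lies in the recorded month or year when rule (B) applies. Two example rows in Table 5-4 would change from 21OCT2001 to 20OCT2001. A lower bound at consent is not needed, and on its own it could move an event out of its recorded month.

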**Table 5-4 Example scenarios**

Partial AE start date	Treatment start date	Relationship with TRTSTD	Imputation Calculation	Imputed Date
12mmyyyy	20OCT2001	Uncertain	NC	<blank>
ddmmm2000	20OCT2001	Before	( D )	01JUL2000
ddmmm2002	20OCT2001	After	( E )	01JAN2002
ddmmm2001	20OCT2001	Uncertain	( B )	21OCT2001
ddSEP2001	20OCT2001	Before	( C )	15SEP2001
ddOCT2001	20OCT2001	Uncertain	( B )	21OCT2001

Partial AE start date	Treatment start date	Relationship with TRTSTD	Imputation Calculation	Imputed Date
ddNOV2001	20OCT2001	After	( A )	01NOV2001

### 5.1.3 Concomitant medication date imputation

#### 5.1.3.1 Prior therapies date imputation

**Start date:** The same rule which is applied to the imputation of AE/concomitant medication start date will be used with the exception that: for scenario (B) will be replaced to be start date of study drug -1.

**End date:**

- Imputed date = min (reference end date, DEC 31), if month and day are missing.
- Imputed date = min (reference end date, last day of the Month), if day is missing.
- Reference end date will be start date of study drug.

If the end date is not missing and the imputed start date is after the end date, use the end date as the imputed start date. If both the start date and the end date are imputed and if the imputed start date is after the imputed end date, use the imputed end date as the imputation for the start date

#### 5.1.3.2 Post therapies date imputation

**Start date:**

- If Day is missing, then impute to the max (reference start date, first day of the month).
- Day and month are missing then impute to the max(reference start date, Jan 1)
- Reference start date will be last date of study treatment administration + 1.

**End date:** No imputation

#### 5.1.3.3 Other imputations

##### Incomplete date of initial diagnosis of cancer and date of most recent recurrence

Missing day is defaulted to the 15th of the month and missing month and day is defaulted to 01-Jan.

##### Incomplete assessment dates for tumor assessment

All investigation dates (e.g. MRI scan, CT scan) must be completed with day, month and year. If one or more assessment dates are incomplete but other investigation dates are available, this/these incomplete date(s) are not considered for calculation of the assessment date and assessment date is calculated as the latest of all investigation dates (e.g. MRI scan, CT scan) if the overall response at that assessment is CR/PR/SD/UNK. Otherwise – if overall response is progression – the assessment date is calculated as the earliest date of all investigation dates at

that evaluation number. If all measurement dates have no day recorded, the 1st of the month is used. If the month is not completed, for any of the investigations, the respective assessment will be considered to be at the date which is exactly between previous and following assessment. If a previous and following assessment is not available, this assessment will not be used for any calculation.

## **5.2 AEs coding/grading**

Adverse events are coded using the Medical dictionary for regulatory activities (MedDRA) terminology.

AEs will be assessed according to the Common Terminology Criteria for Adverse Events (CTCAE) version 4.03.

The CTCAE represents a comprehensive grading system for reporting the acute and late effects of cancer treatments. CTCAE grading is by definition a 5-point scale generally corresponding to mild, moderate, severe, life threatening, and death. This grading system inherently places a value on the importance of an event, although there is not necessarily proportionality among grades (a grade 2 is not necessarily twice as bad as a grade 1). The CTCAE grade of 5 (death) is not used; rather, ‘fatal’ is collected as AE outcome and death information is also collected on a separate (e)CRF page.

## **5.3 Laboratory parameters derivations**

Not applicable.

## **5.4 Statistical models**

Not applicable.

**Document History - Changes compared to previous version**

Version	Date	Changes
---------	------	---------

## **1 General guidance**

### **1.1 Document headers**

The following header will be used for all tables, listings and figures in sections 14 and 16 outlined in this document: CDRB436B2202

### **1.2 Presentation of table numbering and titles within this document**

In practice, the numbering and title for all tables and listings in sections 14 and 16 defined in this document will be of the following formats respectively:

```
Table XX.X-X.X  
Title Title Title Title Title Title  
Population  
Listing XX.X-X.X  
Title Title Title Title Title Title  
Population
```

### **1.3 Treatment group labels and ordering**

The following treatment labels will be used for all tables, listings and figures in the order provided here:

- Treatment group label 1  
Cohort A Cohort B All subjects

### **1.4 Distribution logistics**

Details on in-text tables are added in section 3.1

### **3 Shells and specification**

#### **3.1 Shells and specifications for sections 10, 11 and 12 of the CSR (Text tables and figures)**

##### **Section 10 Study Subjects**

###### **Table 10-1 Subject disposition (FAS)**

Please use the same shell as [Table 14.1-1.1](#)

Source: Table 14.1-1.1

###### **Table 10-2 Analysis set (FAS)**

Please use the same shell as [Table 14.1-2.1](#)

Source: Table 14.1-2.1

**Section 11 Efficacy and/or PK/PD evaluation (also Health Economics, QoL etc.)**

**Table 11-1 Demographic (FAS)**

Please use the same shell as [Table 14.1-3.1](#)

Source: Table 14.1-3.1

## **Section 12 Safety evaluation**

### **Table 12-1 Duration of exposure to study drug (Safety Set)**

Please use the same shell as [Table 14.3-1.1](#)

Source: Table 14.3-1.1

**Table 12-2 Overview of adverse events (Safety set)**

Category	Cohort A N=xx		Cohort B N=xx		All subjects N=xx	
	All grades n (%)	Grade ≥ 3 n (%)	All grades n (%)	Grade ≥ 3 n (%)	All grades n (%)	Grade ≥ 3 n (%)
Adverse events	xx (xx.x)	xx (xx.x)	xx (xx.x)	xx (xx.x)	xx (xx.x)	xx (xx.x)
Treatment-related	xx (xx.x)	xx (xx.x)	xx (xx.x)	xx (xx.x)	xx (xx.x)	xx (xx.x)
SAEs	xx (xx.x)	xx (xx.x)	xx (xx.x)	xx (xx.x)	xx (xx.x)	xx (xx.x)
Treatment-related	xx (xx.x)	xx (xx.x)	xx (xx.x)	xx (xx.x)	xx (xx.x)	xx (xx.x)
Fatal SAEs	xx (xx.x)	xx (xx.x)	xx (xx.x)	xx (xx.x)	xx (xx.x)	xx (xx.x)
Treatment-related	xx (xx.x)	xx (xx.x)	xx (xx.x)	xx (xx.x)	xx (xx.x)	xx (xx.x)
AEs leading to discontinuation	xx (xx.x)	xx (xx.x)	xx (xx.x)	xx (xx.x)	xx (xx.x)	xx (xx.x)
Treatment-related	xx (xx.x)	xx (xx.x)	xx (xx.x)	xx (xx.x)	xx (xx.x)	xx (xx.x)

Numbers (n) represent counts of subjects.

A subject with multiple severity grades for an AE is only counted under the maximum grade.

MedDRA version <xx.x>, CTCAE version <x.xx>.

Source: Table 14.3.1-1.11

**Table 12-3 Adverse events, regardless of study drug relationship by primary system organ class, maximum severity and treatment group (Safety Set)**

Primary system organ class	Cohort A (N=xxx)		Cohort B (N=xxx)		All Subjects (N=xxx)	
	All grades	Grade ≥3	All grades	Grade ≥3	All grades	Grade ≥3
	n (%)	n (%)	n (%)	n (%)	n (%)	n (%)
-Total	xx (xx.x)	xx (xx.x)	xx (xx.x)	xx (xx.x)	xx (xx.x)	xx (xx.x)
Cardiac disorders	xx (xx.x)	xx (xx.x)	xx (xx.x)	xx (xx.x)	xx (xx.x)	xx (xx.x)
xxxxxxxxxxxxxxxxxxxxxxxx	xx (xx.x)	xx (xx.x)	xx (xx.x)	xx (xx.x)	xx (xx.x)	xx (xx.x)
xxxxxxxxxxxxxxxxxxxxxxxx	xx (xx.x)	xx (xx.x)	xx (xx.x)	xx (xx.x)	xx (xx.x)	xx (xx.x)
xxxxxxxxxxxxxxxxxxxxxxxx	xx (xx.x)	xx (xx.x)	xx (xx.x)	xx (xx.x)	xx (xx.x)	xx (xx.x)
xxxxxxxxxxxxxxxxxxxxxxxx	xx (xx.x)	xx (xx.x)	xx (xx.x)	xx (xx.x)	xx (xx.x)	xx (xx.x)
xxxxxxxxxxxxxxxxxxxxxxxx	xx (xx.x)	xx (xx.x)	xx (xx.x)	xx (xx.x)	xx (xx.x)	xx (xx.x)
xxxxxxxxxxxxxxxxxxxxxxxx	xx (xx.x)	xx (xx.x)	xx (xx.x)	xx (xx.x)	xx (xx.x)	xx (xx.x)
xxxxxxxxxxxxxxxxxxxxxxxx	xx (xx.x)	xx (xx.x)	xx (xx.x)	xx (xx.x)	xx (xx.x)	xx (xx.x)

- Primary system organ class is sorted in descending frequency, as reported in "All Subjects" and "All grades".
- A subject with multiple occurrences of an AE is counted only once in the AE category.
- A subject with multiple adverse events is counted only once in the total row.
- MedDRA version <xx.x> has been used for the reporting.

Source:  
14.3.1-1.1

Table

**Table 12-4 Adverse events, regardless of study drug relationship by preferred term, maximum severity and treatment group (Safety Set)**

Preferred term	Cohort A (N=xxx)		Cohort B (N=xxx)		All Subjects (N=xxx)	
	All grades	Grade ≥3	All grades	Grade ≥3	All grades	Grade ≥3
	n (%)	n (%)	n (%)	n (%)	n (%)	n (%)
-Total	xx (xx.x)	xx (xx.x)	xx (xx.x)	xx (xx.x)	xx (xx.x)	xx (xx.x)
Angina pectoris	xx (xx.x)	xx (xx.x)	xx (xx.x)	xx (xx.x)	xx (xx.x)	xx (xx.x)
Oedema NOS	xx (xx.x)	xx (xx.x)	xx (xx.x)	xx (xx.x)	xx (xx.x)	xx (xx.x)
Oedema lower limb	xx (xx.x)	xx (xx.x)	xx (xx.x)	xx (xx.x)	xx (xx.x)	xx (xx.x)
Bradycardia NOS	xx (xx.x)	xx (xx.x)	xx (xx.x)	xx (xx.x)	xx (xx.x)	xx (xx.x)
Oedema peripheral	xx (xx.x)	xx (xx.x)	xx (xx.x)	xx (xx.x)	xx (xx.x)	xx (xx.x)
Sinus bradycardia	xx (xx.x)	xx (xx.x)	xx (xx.x)	xx (xx.x)	xx (xx.x)	xx (xx.x)
Tachycardia NOS	xx (xx.x)	xx (xx.x)	xx (xx.x)	xx (xx.x)	xx (xx.x)	xx (xx.x)

Preferred term is sorted in descending frequency, as reported in "All Subjects" and "All grades".

- A subject with multiple occurrences of an AE is counted only once in the AE category.
- A subject with multiple adverse events is counted only once in the total row.
- MedDRA version <xx.x> has been used for the reporting.

Source: Table 14.3.1-1.1

**Table 12-5 Adverse events, suspected to be study drug related by preferred term, maximum severity and treatment group (Safety Set)**

Please use the same shell as [Table 12-3](#)

Source: Table 14.3.1-1.2

